### **12.3 Analysis Population**

Subjects who are enrolled but never treated with ibrutinib (eg, due to failure to meet the secondary criteria to continue to ibrutinib treatment) will be included in the primary analysis, which will be performed as an intention-to-treat analysis. However, they will not be counted toward the overall accrual goal of 45 subjects. A planned subset analysis will be performed testing the primary and secondary endpoints in the subset of subjects who receive at least 1 dose of ibrutinib on study.

### **12.4 Accrual estimates**

We performed 36 reduced-intensity allogeneic HCT for AML/ALL at Stanford in calendar year 2014. We will also plan to open this study at UCSF (with [name]) and City of Hope (with [name]). We anticipate accruing 10 to 15 subjects annually at UCSF and 20 subjects annually at City of Hope, based on their historical transplant patterns. We therefore expect that study accrual will take 1 year to complete.

## APPENDICES

### APPENDIX A: Pre-Transplant Eligibility Checklist

Protocol Title:	A Phase 2 Study of Ibrutinib After Reduced-Intensity Conditioning and Allogeneic Hematopoietic Cell Transplantation for Acute Leukemia
Protocol Number:	IRB-38934 / BMT302
Principal Investigator:	[name]

#### II. Subject Information:

Subject Name/ID:
Gender:  Male  Female

#### III. Study Information:

SRC-Approved  IRB-Approved  Contract signed

#### IV. Inclusion/Exclusion Criteria

**Pre-transplant screening: all studies to be completed within 60 days of beginning conditioning therapy, unless otherwise indicated:**

Inclusion Criteria (From IRB-approved protocol)	Yes	No	Supporting Documentation*
1. Diagnosis of acute myeloid leukemia (AML), acute biphenotypic leukemia, or acute lymphoblastic leukemia (ALL). (CML transformed to blast crisis is eligible).			
2. Planned allogeneic HCT using FLU/MEL or FLU/BU conditioning (as defined in protocol).			
3. Planned GvHD prophylaxis with TAC/MTX or TAC/SRL (regimens defined in protocol).			
4. HLA-identical sibling donor, HLA-matched unrelated donor, or donor mismatched at 1 HLA allele or antigen.			
5. Less than or equal to 5% blasts on bone marrow examination within 60 days of starting conditioning.			
6. Age $\geq$ 18 years and $\leq$ 70 years.			
7. Able to give informed consent.			

Exclusion Criteria (From IRB-approved protocol)	Yes	No	Supporting Documentation*
1. Active involvement of the central nervous system with malignancy (previous CNS involvement is allowed if clearance of CNS disease has been documented prior to enrollment)			
2. Pregnant or breastfeeding			
3. Karnofsky Performance Status <60%			
4. Active leukemia (> 5% leukemic blasts in peripheral blood or bone marrow)			
5. Non-hematologic malignancy with life expectancy < 5 years			
6. HIV positivity, active hepatitis C virus infection, or active hepatitis B virus infection. (Subjects positive for HBV surface antigen or HBV core antibody are eligible if they have a negative HBV PCR before enrollment. Those who are PCR-positive are not eligible)			
7. Known bleeding disorder (eg, von Willebrand's disease, hemophilia)			
8. History of other malignancies, except: 
 
o Malignancy treated with curative intent and with no known active disease for at least 3 years before the first dose of study drug, and felt to be at low risk of recurrence by treating physician
 
o Adequately treated non-melanomatous skin cancer or lentigo maligna without evidence of disease
 
o Adequately treated carcinoma in situ without evidence of invasive disease
 
			

\*All subject files must include supporting documentation to confirm subject eligibility. The method of confirmation can include, but is not limited to, laboratory test results, radiology test results, subject self-report, and medical record review.

**II. Subject Information:**

Subject Name/ID:
Gender:  Male  Female

**III. Study Information:**

SRC-Approved  IRB-Approved  Contract signed

**IV. Continuation Criteria**

Continuation Criteria (From IRB-approved protocol)	Yes	No	Supporting Documentation*
1. Between Day +60 and Day +90 after allogeneic HCT			
2. Age $\geq$ 18 years			
3. Adequate hematologic function, defined as ANC $> 0.75 \times 10^9/L$ , platelet count $> 50 \times 10^9/L$ , and hemoglobin $> 8.0 \text{ g/dL}$ without transfusion or growth-factor support for at least 7 days prior to screening (with the exception of pegylated G-CSF and darbepoietin, which require at least 14 days of abstinence before screening)			
4. Adequate hepatic and renal function, defined by serum AST and ALT $\leq 3x$ upper limit of normal (ULN); estimated creatinine clearance $\geq 30 \text{ mL/min}$ by Cockroft-Gault equation; and bilirubin $\leq 1.5 \times \text{ULN}$ (unless elevated bilirubin is due to Gilbert's syndrome or of non-hepatic origin)			
5. Adequate coagulation studies, defined as PT/INT and PTT (aPTT) $\leq 1.5 \times$ upper limit of normal			
6. Female subjects who are of non-reproductive potential (ie, post-menopausal by history - no menses for $\geq 1$ year; OR history of hysterectomy; OR history of bilateral tubal ligation; OR history of bilateral oophorectomy). Female subjects of childbearing potential must have a negative serum pregnancy test upon screening.			

Continuation Criteria (From IRB-approved protocol)	Yes	No	Supporting Documentation*
7. Male and female subjects who agree to use both a highly effective method of birth control (eg, implants, injectables, combined oral contraceptives, some intrauterine devices [IUDs], sexual abstinence, or sterilized partner) and a barrier method (eg, condoms, vaginal ring, sponge, etc) during the period of therapy and for 30 days after the last dose of study drug for females and 90 days after the last dose of the study drug for males.			

Withdrawal Criteria (From IRB-approved protocol)	Yes	No	Supporting Documentation*
1. Active and uncontrolled acute GvHD Grades III or IV			
2. Use of secondary therapy for acute GvHD at any time (defined as any systemic therapy intended to treat acute GvHD besides corticosteroids)			
3. Requirement for anticoagulation with warfarin or other Vitamin K antagonists (concomitant use of other anticoagulants is permitted)			
4. Relapsed leukemia (> 5% leukemic blasts in peripheral blood or bone marrow at any point after allogeneic HCT)			
5. Karnofsky Performance Status <60%			
6. Chemotherapy ≤ 21 days prior to first study drug dose and/or monoclonal antibody ≤ 6 weeks prior to first study drug dose			
7. Vaccinated with live, attenuated vaccine within 4 weeks of first study drug dose			
8. Currently active, clinically significant cardiovascular disease (eg, NYHA Class III or IV heart failure, uncontrolled arrhythmia, or acute coronary syndrome within 6 months of first study drug dose)			
9. History of stroke or intracranial hemorrhage within 6 months of first study drug dose			
10. Any life-threatening illness, medical condition, or organ dysfunction that, in the investigator's judgement, could compromise the subject's safety or put the study outcomes at undue risk.			
11. Major surgery within 4 weeks of first study drug dose			
12. Active, uncontrolled systemic infection			

Withdrawal Criteria (From IRB-approved protocol)	Yes	No	Supporting Documentation*
13. Unresolved toxicities from prior anti-cancer therapy (not resolved to CTCAE v4 Grade 1 or less, or to the levels described in these criteria, except alopecia)			
14. Unable to swallow capsules or malabsorption syndrome, disease significantly affecting gastrointestinal function, or resection of the stomach or small bowel, symptomatic inflammatory bowel disease or ulcerative colitis, or partial or complete bowel obstruction			
15. Requiring treatment with strong CYP3A inhibitor (see Appendix E)			
16. Unwilling or unable to participate in all required study evaluations and procedures			
17. Unable to understand the purpose and risks of the study and to provide a signed and dated informed consent form (ICF) and authorization to use protected health information (in accordance with national and local subject privacy regulations).			
18. Lactating or pregnant			
19. Uncontrolled cardiac arrhythmias			

\*All subject files must include supporting documentation to confirm subject eligibility. The method of confirmation can include, but is not limited to, laboratory test results, radiology test results, subject self-report, and medical record review.

### Appendix C: Grading of acute graft--vs-host disease

Organ	Stage	Description
Skin	1	Maculopapular rash over <25% of body area
	2	Maculopapular rash over 25–50% percent of body area
	3	Generalized erythroderma
	4	Generalized erythroderma with bullous formation and often with desquamation
Liver	1	Bilirubin 2.0–3.0 mg/dL; SGOT 150–750 IU
	2	Bilirubin 3.1– 6.0 mg/dL
	3	Bilirubin 6.1–15.0 mg/dL
	4	Bilirubin > 15.0 mg/dL
Gut	1	Diarrhea > 500 mL/day; or upper-gut symptoms with positive histology
	2	Diarrhea > 1000 mL/day
	3	Diarrhea > 1500 mL/day
	4	Diarrhea > 2000 mL/day; or severe abdominal pain ± ileus

Glucksberg Grade:

- I      Stage 1 or 2 skin involvement; no liver or gut involvement; ECOG PS 0
- II     Stage 1–3 skin involvement; Stage 1 liver or gut involvement; ECOG PS 1
- III    Stage 2–3 skin, liver, or gut involvement; ECOG PS 2
- IV    Stage 1–4 skin involvement; Stage 2–4 liver or gut involvement; ECOG PS 3

Abbreviations: SGOT: serum glutamic oxaloacetic transaminase; ECOG: Eastern Cooperative Oncology Group; PS: performance status.

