#### **3.2.2 Exclusion Criteria (prior to ibrutinib administration)**

- Active and uncontrolled acute GvHD Grades III or IV
- Use of secondary therapy for acute GvHD at any time (defined as any systemic therapy intended to treat acute GvHD besides corticosteroids)
- Requirement for anticoagulation with warfarin or other Vitamin K antagonists (concomitant use of other anticoagulants is permitted)
- Relapsed leukemia (> 5% leukemic blasts in peripheral blood or bone marrow after allogeneic HCT)
- Karnofsky Performance Status < 60%
- Chemotherapy  $\leq$  21 days prior to first administration of study treatment and/or monoclonal antibody  $\leq$  6 weeks prior to first administration of study treatment
- Vaccinated with live, attenuated vaccines within 4 weeks of first dose of study drug.
- Currently active, clinically significant cardiovascular disease, such as uncontrolled arrhythmia or Class 3 or 4 congestive heart failure as defined by the New York Heart Association Functional Classification; or a history of myocardial infarction, unstable angina, or acute coronary syndrome within 6 months prior to randomization.

- History of stroke or intracranial hemorrhage within 6 months prior to screening
- Any life-threatening illness, medical condition, or organ system dysfunction that, in the investigator's opinion, could compromise the subject's safety or put the study outcomes at undue risk.
- Major surgery within 4 weeks of first dose of study drug.
- Any uncontrolled active systemic infection.
- Unresolved toxicities from prior anti-cancer therapy, defined as having not resolved to Common Terminology Criteria for Adverse Event (CTCAE, version 4), Grade ≤ 1, or to the levels dictated in the inclusion/exclusion criteria with the exception of alopecia
- Unable to swallow capsules or malabsorption syndrome, disease significantly affecting gastrointestinal function, or resection of the stomach or small bowel, symptomatic inflammatory bowel disease or ulcerative colitis, or partial or complete bowel obstruction
- Requires treatment with a strong cytochrome P450 (CYP) 3A4/5 inhibitor (see Appendix E).
- Unwilling or unable to participate in all required study evaluations and procedures.
- Unable to understand the purpose and risks of the study and to provide a signed and dated informed consent form (ICF) and authorization to use protected health information (in accordance with national and local subject privacy regulations).

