## 9. STUDY CALENDAR

Studies shown in *italics* are research studies, while evaluations shown in black represent clinical standard of care.

	Within 60 days of starting conditioning	Between Day +28 and Day +60	Start of ibrutinib (between Day +60 and Day +90)	Day +90	Day +180	9 months	1 year	15 months	18 months	2 years	Off Study
Eligibility determination	X	X									
History & physical	X	X	X	X	X	X	X	X	X	X	X
KPS assessment	X	X	X	X	X	X	X	X	X	X	X
Laboratory testing of hepatic and renal function	X	X	X	X	X	X	X	X	X	X	X
Transplant evaluation per institutional criteria	X										
Electrocardiogram (ECG)	X										
Hepatitis and HIV testing	X										
Pregnancy test (for women of childbearing potential)	X										
Bone marrow aspiration and/or biopsy with assessment of minimal residual disease	X	X		AML only*	AML only		AML only				
Minimal residual disease detection by peripheral-blood high-throughput sequencing (ClonoSEQ)	X	X		X*	X		X		X	X	
Assessment of concomitant medications	X	X	X	X	X	X	X	X	X		X
Acute GvHD assessment		X		X							
Chronic GvHD assessment				X	X	X	X	X	X	X	X
Ibrutinib (study drug)						X -----			X		
Adverse event evaluation						X-----				X	
Blood draw for biological studies	X		X	X	X		X		X	X	
Blood sample from HCT donor (related only)	X										

For the Day +90 and Day +180 timepoints, the relevant evaluations may be performed within +/- 2 weeks of the specified timepoint. For the 9-month, 1-year, 15-month, and 18-month timepoints, the relevant evaluations should be performed within +/- 4 weeks of the specified timepoint.

\* Please note: Okay to omit Day +90 MRD testing and Day +90 biopsy if previous biopsy (between Day +28 and Day +60) showed no evidence of disease.

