## **10. MEASUREMENTS**

### **10.1 Primary and Secondary Outcome measures**

The primary outcome measure is the incidence of relapsed leukemia at 18 months after allogeneic HCT. This is an efficacy endpoint.

Secondary endpoints include the incidence of acute GvHD Grades II–IV and III–IV at Day +180 after allogeneic HCT, the incidence of chronic GvHD at 18 months after allogeneic HCT, and the incidence of detectable minimal residual disease at 1 year after allogeneic HCT.

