#### **10.1.2 Measurement Definition**

For the primary outcome measure, relapsed leukemia is defined as > 5% leukemic blasts detected in bone marrow or peripheral blood. Subjects will also be considered to have relapsed leukemia if they receive any active treatment for progressive leukemia after allogeneic HCT, even if they have <5% leukemic blasts. Withdrawal of immunosuppression alone is not considered an active treatment for progressive disease.

For the secondary outcome measures, acute GvHD will be graded and scored according to standard criteria (Appendix C). Chronic GvHD will be graded and scored according to the 2014 NIH consensus criteria (Appendix D). Minimal residual disease will be assessed by high-throughput sequencing (ClonoSEQ) for subjects with ALL, and by high-sensitivity flow cytometry for subjects with AML or acute biphenotypic leukemia. Minimal residual disease will be considered present if  $> 1 \times 10^{-6}$  leukemic clones are detected by ClonoSEQ (20), or if any aberrant blasts matching the original leukemic immunophenotype are detected by high-sensitivity flow cytometry (21).

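### Appendix C does not give each acute GvHD organ-stage profile exactly one grade, so the Grade II–IV and III–IV secondary endpoints are partly undefined

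*Combined protocol and SAP*

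**What the plan says.** Section 10.1 states: "Secondary endpoints include the incidence of acute GvHD Grades II–IV and III–IV at Day +180 after allogeneic HCT". Section 10.1.2 says how they are scored: "acute GvHD will be graded and scored according to standard criteria (Appendix C").

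Appendix C stages skin, liver and gut from 1 to 4 and then gives four overall grades:

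- Grade I: "Stage 1 or 2 skin involvement; no liver or gut involvement; ECOG PS 0"
- Grade II: "Stage 1–3 skin involvement; Stage 1 liver or gut involvement; ECOG PS 1"
- Grade III: "Stage 2–3 skin, liver, or gut involvement; ECOG PS 2"
- Grade IV: "Stage 1–4 skin involvement; Stage 2–4 liver or gut involvement; ECOG PS 3"

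The appendix does not say whether a semicolon means *and* or *or*, whether the ECOG value is a requirement, or which grade applies when two fit.

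For performance status, the Study Calendar has a row for "KPS assessment", and Section 4 also names Karnofsky. Section 10.1.3 has acute GvHD scored weekly through Day +100, with no performance status attached to that scoring. Appendix D's chronic GvHD form matches ECOG 0, 1 and 2 to Karnofsky 100, 80–90 and 60–70, and puts ECOG 3 and 4 together below 60. That form is completed only after a chronic GvHD diagnosis, and Appendix C does not refer to it.

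The same grades are used in the pre-ibrutinib exclusion in Section 3.2.2, "Active and uncontrolled acute GvHD Grades III or IV", which Appendix B repeats.

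**The concern.** A grading rule for an endpoint must place every affected patient in one grade and only one. Two cuts matter here: I against II for the first endpoint, and II against III for the second. If a profile fits grades on both sides of a cut, the scorer decides whether the patient has the event. If a profile fits no grade, the patient drops out of both counts even when the disease is severe. Section 12.4 plans three centers, and each would have to settle the table for itself. The Section 3.2.2 exclusion also uses Grades III and IV, so the ambiguity reaches one of the criteria that decide who joins the treated subset analyzed under Section 12.3.

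**Working it through.** The plan gives no figure to reproduce. The check lists every possible profile and applies the four lines to each.

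**Inputs.** Skin, liver and gut each take stage 0 to 4, which gives 5 × 5 × 5 − 1 = 124 profiles with some involvement. The grade lines are those of Appendix C.

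**Reading 1: semicolon means *and*, ECOG ignored.** Grade I is skin 1–2 with no liver or gut. Grade II is skin 1–3 with liver or gut at Stage 1. Grade III is any organ at Stage 2–3. Grade IV is any skin involvement with liver or gut at Stage 2–4. Two points are open: whether Grade II still applies when the other of liver and gut is above Stage 1, and whether a Stage 4 organ bars Grade III.

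| Variant | No grade | One | Two | Three | Straddle III–IV | Straddle II–IV |
|---|---|---|---|---|---|---|
| Grade II loose, Stage 4 does not bar III | 12 | 29 | 67 | 16 | 25 | 1 |
| Grade II strict, Stage 4 does not bar III | 12 | 31 | 81 | 0 | 7 | 1 |
| Grade II strict, Stage 4 bars III | 16 | 65 | 43 | 0 | 7 | 1 |

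- *Gaps.* Eight of the 12 have no skin involvement: every combination of liver and gut at stages 0, 1 or 4 except both 0 (3 × 3 − 1 = 8). These include isolated Stage 1 and isolated Stage 4 liver or gut. The other four are Stage 4 skin with liver and gut each at 0 or 1 (2 × 2 = 4). If Stage 4 bars Grade III, four more appear: no skin, one of liver and gut at Stage 4 and the other at 2 or 3.
- *Straddling III–IV.* Seven do so on either reading of Grade II: skin 2 alone (I and III), and skin 2 or 3 with Stage 1 liver, gut or both (II and III; 2 × 3 = 6). The loose Grade II adds skin 1, 2 or 3 with one of liver and gut at Stage 1 and the other at 2, 3 or 4 (3 × 2 × 3 = 18), and 7 + 18 = 25.
- *Straddling II–IV.* Only skin 2 alone.
- *Harmless ties.* The remaining double grades are III against IV: 67 + 16 − 25 = 58, 81 − 7 = 74 and 43 − 7 = 36 in the three rows.

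**Reading 2: semicolon between organ clauses of Grades II and IV means *or*, ECOG ignored.** Grade I is left as it is, since it says that liver and gut are clear. No profile is ungraded, but 10 fit one grade, 39 two, 74 three and 1 four. So 39 + 74 + 1 = 114 of 124 fit more than one. Ninety are ambiguous for III–IV and two for II–IV. Stage 1 skin alone fits I, II and IV.

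**Reading 3: ECOG required.** Each line has its own ECOG value, so no combination can fit two grades. With ECOG 0–3 there are 124 × 4 = 496 combinations, and each match of a profile to a grade holds at one ECOG value only.

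- *And*, first row: 29 + 2 × 67 + 3 × 16 = 211 graded, 496 − 211 = 285 ungraded (57%).
- *And*, third row: 65 + 2 × 43 = 151 graded, 496 − 151 = 345 ungraded (70%).
- *Or*: 10 + 2 × 39 + 3 × 74 + 4 × 1 = 314 graded, 496 − 314 = 182 ungraded (37%).

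Stage 2 skin alone shows the effect under *and*: Grade I at ECOG 0, no grade at ECOG 1, Grade III at ECOG 2, no grade at ECOG 3. ECOG 4 appears in no line.

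**The case against.** The strongest reply is that the table works for most purposes. Most double grades under *and* are III against IV, which changes neither endpoint nor the Section 3.2.2 exclusion. Stage 4 gut or liver with any skin involvement is Grade IV under *and* when ECOG is set aside. All of this stands, and it is why the size is given by straddling profiles and gaps, not by the total of double grades.

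A reader might infer more than the documents support:

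- *That ECOG is unobtainable.* Karnofsky is scheduled, and Appendix D's conversion yields ECOG 0 to 2. What remains is that Appendix C does not invoke it, ECOG 3 and 4 are not separated, and nothing is scheduled at the weekly scoring.
- *That gaps, overlaps and a missing ECOG all apply together.* They do not. If ECOG binds, overlaps vanish; if it does not, its absence does no harm. With ECOG set aside, gaps need *and*.
- *That common presentations cannot be scored.* The documents give no frequencies.
- *That entry to the treated subset is wholly undefined.* Other criteria cover some ungraded cases: Section 3.1.2 caps bilirubin at 1.5 × ULN, with exceptions for Gilbert's syndrome and non-hepatic causes, and Section 3.2.2 excludes serious gastrointestinal disease and prior second-line therapy for acute GvHD.

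It can also be said that the table sits under the name of a published scale, which sites know. But the text printed there is the rule that Section 10.1.2 invokes, and nothing says which version prevails.

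**Conclusion.** The point holds for the two acute GvHD secondary endpoints. With ECOG set aside, no literal reading of Appendix C gives every profile one grade. Under *and*, 12 to 16 of 124 profiles have none, 7 to 25 straddle the III–IV endpoint and one straddles II–IV. Under *or*, with the literal wording, 114 fit more than one grade and 90 are ambiguous for III–IV. A binding ECOG replaces the overlaps with gaps: 285 to 345 of 496 combinations under *and*.

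These figures count profiles with equal weight. They say nothing about how many of the planned 50 patients would be affected, which cannot be worked out from the documents. The relapse endpoint and the NRM stopping rule do not use these grades. The matter is worth correcting before the endpoints are scored, but it does not threaten the main conclusion of the trial.

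**What to change.** Keep the organ-stage table. Replace the four grade lines with one organ-stage rule that covers every profile once, including isolated organ involvement and Stage 4 disease, states that the highest grade met applies, and does not require a performance status. Record the three organ stages on the CRF at each assessment and derive the grade by program for both endpoints. Before adoption, run the rule over all 124 profiles to confirm one grade each.

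A highest-grade rule added to the present lines is not enough: under *and* the 12 to 16 gaps remain, and under *or* Stage 1 skin alone becomes Grade IV.

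The sponsor should choose the published mapping. Because the choice can move profiles across the II/III cut, it must be reconciled with the Grade III–IV criterion in Section 3.2.2 and the matching item in Appendix B; this review does not say where that cut belongs.

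The cost is a short amendment, one appendix table and one CRF derivation, with no new visits or tests. Sites must record stages instead of only an overall grade.
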